1.1 Objectives and Hypotheses

The main objective of the SHAPE pilot study is to determine the feasibility of using Habit Formation (HF) treatment to increase Physical Activity (PA) (reduction in daily in hours of sedentary time), and dietary among prefrail African Americans. This study will test two hypotheses:

***Hypothesis 1:** The SHAPE study will demonstrate good feasibility with high recruitment rate and successfully administrating all of measures among the target population.*

***Hypothesis 2:** Treatment group participants will demonstrate greater increases in primary outcomes (sedentary time and dietary quality) and secondary outcomes (prefrailty reduction, lower extremity strength, balance, and quality of life) at intervention completion.*

[figure not shown]

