1.3.1 Participants eligibility

The inclusion criteria of participants includes: (a) English-speaking, (b) community dwelling, (c) members of PRP registry, (d) prefrail (evaluated by the Fried's Frailty Criteria Index), (e) self-identify as African Americans, (f) aged 55 and older. The exclusion criteria include: (a) diagnosed psychiatric disorders, (b) moderate or severe cognitive impairment (verified using the validated 6CIT and operationalized as score of ≥ 10),⁶⁸⁻⁶⁹ the use of prescription drugs that could affect cognition and functioning (e.g., neuroleptics), (c) individuals with typical daily pain ratings of $\geq 7/10$, (d) plan to change residences during the study period; (b) rely on a wheelchair for home or community mobility; (e) are actively receiving home care services, occupational, or

physical therapy; (f) are on dialysis or who have an end stage disease (e.g., stage IV heart failure); (g) are enrolled in a health promotion program focused on PA and diet; and (h) those who have a baseline dietary quality score of $\geq 85/100$ as their diet would already be very close to ideal (average score for U.S. population = 59).

Figure 2. Overview of the SHAPE pilot study.

Raters will conduct the activities in the navy boxes.

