1.3.8 Follow-up data collection

When the 12-week intervention period is over, the coordinator will assign raters for follow-up evaluation. Most of the measures will be re-administered.

Table 1 Overview of measurements and testing time

Evaluation time point (week)	Variable	Measure
Screening		
Phone screening (w0)	Eligibility	1. Phone screening eligibility form
	Frailty status	2. Paulson Lichtenberg Frailty Index (PLFI)
	Cognitive impairment	3. The Six Item Cognitive Impairment Test (6CIT)
Primary outcome*		
Baseline (w1), follow-up (w15)	Sedentary time	4. Community Healthy Activities Model Program for Seniors (CHAMPS)
Baseline evaluation (w1- 2), follow-up (w15)	Sedentary time	5. ActivPal kcal expenditure
Baseline (w1, 2 nd phone follow-up), follow-up (w15, 2 nd phone follow-up)	Dietary quality	6. Automated Self-Administered 24-hour (ASA24) dietary recall
Secondary outcome		
Baseline (w1), follow-up (w15)	Frailty status	7. The Fried's Frailty Criteria 
 • Grip strength with dynamometer • 15 ft walking test
	Lower extremity muscle strength	8. Short Physical Performance Battery (SPPB) 
 • 3-meter walking test
	Balance	
	Quality of life	9. The World Health Organization Quality of Life- BREF (WHOQOL-BREF)
Habit formation (Treatment group only)	Habit formation	10. The self-reported habit index subscale
Demographics and other mediators		
Baseline (w1)	Comorbidities	11. Comorbidity Checklist
	Sociodemographic	12. Sociodemographic Form
Baseline (w1), follow-up (w15)	Participants anthropologies	13. Participants anthropologies forms 
 • Weight • Height • Waist circumference
	Depressive symptoms	14. Geriatric Depression Short form (GDS)
Treatment session 1,3,5,7,9 (w 3, 5, 7, 9, 11)	Habit formation	15. Self-report habit index (SRHI)

Note. *Both primary outcomes will be used for screening potential participants' eligibility.

2. Data analysis plan

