2.1 Data analysis

Feasibility outcomes such as recruitment, retention, and attendance data were presented by descriptive statistics. Differences in baseline characteristics between the two groups were tested by independent t tests or chi-square/Fisher's exact tests. For the primary and secondary outcomes, effect sizes were represented by Cohen's D, where 0.2 indicates small, 0.5 as moderate, and 0.8 as large effects. As for mechanisms of behavior change, pre and post habit formation effect sizes are estimated by Cohen's D. All statistical analyses were conducted by IBM SPSS software, version 26.0 (SPSS Inc., Chicago, IL).

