2.3 Assessments

Primary outcomes (measured at week 0 and 1 week post intervention). Sedentary Time (ST) was measured via the ActivPal wireless activity tracker. ActivPal is a validated tool with a commercialized program to generate mean minutes of total ST (min/day), sum of 30-minute bouts ST, and sum of 60-minunite bouts ST, as well as the number of 30-min bout ST and 60-minutes bout ST per day. Participants wore the ActivPal device on their thigh for seven days during their waking hours. Dietary Quality was measured using the Healthy Eating Index (HEI) and operationalized as the total HEI score generated from the National Cancer Institute's ASA 24®.

Secondary outcomes (measured at week 0 and 1 week post intervention). Pre-frailty status was measured using the current gold standard, the Cardiovascular Health Study frailty criteria as composite index consisting of the following components: (a) self-reported weight maintenance; (b) walking speed (the mean time of two trials for the time taken to walk 15 ft. reported in seconds); (c) grip strength, (mean score of grip strength reported in Lbs. of three trials on the dominant hand using a calibrated Jaymar dynamometer); (d) exhaustion, measured as a response of "All of the time" or "Most of the time" to the following two questions reported on a 4 point Likert scale, "I felt that everything I did was an effort in the last week," and "I could not get going in the last week"; and (e) total Kcals of energy expended over a 7 day period, measured via Community Healthy Activities Model Program for Seniors (CHAMPS) questionnaire. Change of all PA and MVPA duration (minutes/week) measured by CHAMPS. We also used Activpal to estimate the cumulated MVPA duration. We cumulated MVAP minutes by selecting activity intensity greater than 3 METs. Physical Function was measured via the Short Physical Performance Battery (SPPB) subtests for lower extremity strength and balance. Depressive symptoms were measured using the Geriatric Depression Scale (Kieffer & Reese, 2002). Participant anthropometry such as weight circumference (inch) was measured by a girthometer, height (cm) by a stadiometer, and weight (pound) by medical scales. Body mass index (BMI) was also calculated based on participant anthropometry. Quality of life was measured using the 26-item validated WHOQOL-BREF. Occupational performance was

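### Hypothesis 2 outcomes are reported only as a labelled Cohen's d; a baseline-adjusted between-arm difference with a 95% CI can be had from data already planned

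*Combined protocol and SAP*

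**What the plan says.** Hypothesis 2 in section 1.1 compares the arms at intervention completion: "Treatment group participants will demonstrate greater increases in primary outcomes (sedentary time and dietary quality", followed by prefrailty, lower extremity strength, balance and quality of life. It is one of two hypotheses that the study says it will test.

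The analysis of those outcomes is one sentence in section 2.1: "For the primary and secondary outcomes, effect sizes were represented by Cohen's D, where 0.2 indicates small, 0.5 as moderate, and 0.8 as large effects". The section does not say whether d compares the arms at follow-up, compares them on change, or is taken within an arm. The next sentence uses the same statistic for a pre-post contrast in habit formation, so the contrast cannot be taken for granted. The only between-group tests named are for baseline characteristics.

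Section 2.3 shows that baseline values will exist: "Primary outcomes (measured at week 0 and 1 week post intervention" and "Secondary outcomes (measured at week 0 and 1 week post intervention". The primary outcomes have natural units. The ActivPal software will "generate mean minutes of total ST (min/day), sum of 30-minute bouts ST" and further bout measures, and diet is the total HEI score.

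**The concern.** A d with a size word attached gives a point estimate and no measure of its uncertainty. In a trial this small, the word can suggest a finding where the data are compatible with no effect or with one in the other direction. If the denominator is not stated, another analyst cannot reproduce the d, and the planners of a later trial cannot turn it back into minutes per day or HEI points. The planned measurements already allow a better-defined estimate, so the loss is avoidable.

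**Working it through.** **Inputs.** Cut-offs 0.2, 0.5 and 0.8 (section 2.1). Size: 15 per group (section 2.2), or 80 randomised 1:1, so 40 per arm (sections 1.3 and 1.3.5). Baseline and follow-up values are planned (section 2.3). The documents give no SD and no baseline-follow-up correlation r; r = 0.3, 0.5 and 0.8 is an assumed range. Equal SDs at both visits, full retention and two-sided 95% intervals are also assumed. The 15 per group is not derived from any inputs, so there is no stated calculation to reproduce.

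**Step 1: interval around an observed d.** With n per arm, t = d x sqrt(n/2) on 2n - 2 degrees of freedom; the limits come from inverting the noncentral t. At n = 15, d = 0.5 gives t = 0.5 x sqrt(7.5) = 1.37 on 28 df. At n = 40 it gives t = 0.5 x sqrt(20) = 2.24 on 78 df.

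| Observed d | 95% CI, 15 per arm | 95% CI, 40 per arm |
|---|---|---|
| 0.2 | -0.52 to 0.92 | -0.24 to 0.64 |
| 0.5 | -0.23 to 1.22 | 0.05 to 0.94 |
| 0.8 | 0.05 to 1.54 | 0.34 to 1.25 |

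If the true effect is zero, the chance that |d| reaches a cut-off c is twice the upper tail of the central t at c x sqrt(n/2). For 0.2 this is 59% at 15 per arm and 37% at 40; for 0.5 it is 18% and 3%.

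**Step 2: denominator.** With equal SDs at the two visits, the change-score SD is sqrt(2(1 - r)) times the raw SD. A between-arm difference of 0.5 raw SD is therefore d = 0.5 / sqrt(2(1 - r)) on the change-score SD:

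- r = 0.3: 0.5 / sqrt(1.4) = 0.42
- r = 0.5: 0.5 / sqrt(1.0) = 0.50
- r = 0.8: 0.5 / sqrt(0.4) = 0.79

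**Step 3: baseline adjustment.** Half-widths of the 95% CI for the difference, in SD units, at n = 15:

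- Follow-up only: t(28) x sqrt(2/15) = 0.748
- Change score: 0.748 x sqrt(2(1 - r))
- ANCOVA: t(27) x sqrt((2/15)(1 - r^2)(1 + 1/26)), where the last factor allows for chance baseline imbalance

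| r (assumed) | Follow-up only | Change score | ANCOVA | ANCOVA narrower than change score | ANCOVA narrower than follow-up only |
|---|---|---|---|---|---|
| 0.3 | 0.748 | 0.885 | 0.728 | 17.7% | 2.6% |
| 0.5 | 0.748 | 0.748 | 0.661 | 11.6% | 11.6% |
| 0.8 | 0.748 | 0.473 | 0.458 | 3.2% | 38.8% |

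At 40 per arm the ANCOVA half-widths are 0.428, 0.388 and 0.269, against 0.527, 0.445 and 0.282 for change scores and 0.445 for follow-up only. The relative gains are similar. Percentages are from unrounded half-widths.

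**The case against.** The strongest defence is that this is a feasibility pilot: section 1.1 makes feasibility the main objective, and section 2.2 says the size was not set to determine efficacy. A descriptive effect size may seem enough. But an interval needs no power calculation, and a study not sized for efficacy has all the more reason to show its uncertainty.

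A second defence is that Hypothesis 2 speaks of greater increases, and section 2.3 expresses the CHAMPS activity durations as change. A between-arm comparison of change already uses the baseline, so ANCOVA may add little. This largely stands. The fair comparator for ANCOVA is the change score, and the gain of up to 39% over follow-up only should not be the headline. Which SD serves as denominator is also a matter of choice; what is missing is the statement of it.

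A reader might infer two stronger points that the documents do not support:

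- **That every small or moderate label hides an interval containing zero.** For d = 0.5 this is true at 15 per arm and false at 40, and the documents leave the size unresolved.
- **That entry limits narrow the baseline spread enough to turn a moderate d into a large one.** Table 1 notes "Both primary outcomes will be used for screening potential participants' eligibility", but section 1.3.1 gives no sedentary-time limit. For diet it excludes "those who have a baseline dietary quality score of" 85 or more out of 100, beside a US average of 59. Under a normal model centred at 59, that cut-off leaves about 91% to 98% of the SD for assumed SDs of 15 to 10, so the narrowing is slight. With equal SDs, the highest value in the assumed range, 0.79, is still below the plan's large cut-off.

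**Conclusion.** The point holds and should be fixed. The missing interval and the unstated contrast and denominator are the main defect, and they matter at either sample size. An observed d of 0.2 is compatible with zero at both 15 and 40 per arm; an observed d of 0.5 is so only at 15. The same difference of 0.5 SD can be reported as anything from 0.42 to 0.79, depending on an undeclared SD, over the assumed r of 0.3 to 0.8.

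Baseline adjustment is a low-cost improvement with an uncertain yield: at 15 per arm, about 3% to 18% narrower than change scores and 3% to 39% narrower than follow-up only. These figures rest on the assumed r, equal SDs and full retention; loss to follow-up would widen every interval. Trial conduct is not affected.

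**What to change.** Amend section 2.1 as follows.

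- **Contrast and model.** State that the contrast is treatment versus control. For each continuous outcome measured in both arms at both visits, regress the follow-up value on arm and the baseline value of that outcome (ANCOVA), with participants analysed as randomised.
- **Main result.** Report the adjusted difference in natural units with a 95% CI and the number analysed per arm. Name the sedentary-time measure it refers to, since Table 1 and section 2.3 list several.
- **Effect size.** Give a between-arm d with its 95% CI as a secondary scale. Name its denominator in advance, and its sign, because the aim is to reduce sedentary time.
- **Frailty category.** Everyone enters prefrail, so there is no baseline category to adjust for. Give counts by arm and a risk difference for becoming non-frail, with a small-sample 95% CI (for example, Newcombe).
- **Treatment-only measures.** Report these as within-arm change.
- **Sample size.** Reconcile sections 1.3 and 2.2, since precision depends on which figure applies.

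The cost is SAP wording and a few lines of code in the software already named ("All statistical analyses were conducted by IBM SPSS software, version 26.0"), with no new data, visits or participants. There are three downsides. The gain in precision may be small. Intervals will look less favourable than labels. And because section 2.1 is written in the past tense, the adjusted analysis must be labelled post hoc if the outcomes have already been analysed.

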2.2 Sample size estimation

We did not use power analysis to estimate study sample size for determine efficacy. We aim to recruit 15 participants in per group suggested for feasibility pilot study.

2.3 Assessments

Primary outcomes (measured at week 0 and 1 week post intervention). Sedentary Time (ST) was measured via the ActivPal wireless activity tracker. ActivPal is a validated tool with a commercialized program to generate mean minutes of total ST (min/day), sum of 30-minute bouts ST, and sum of 60-minunite bouts ST, as well as the number of 30-min bout ST and 60-minutes bout ST per day. Participants wore the ActivPal device on their thigh for seven days during their waking hours. Dietary Quality was measured using the Healthy Eating Index (HEI) and operationalized as the total HEI score generated from the National Cancer Institute's ASA 24®.

Secondary outcomes (measured at week 0 and 1 week post intervention). Pre-frailty status was measured using the current gold standard, the Cardiovascular Health Study frailty criteria as composite index consisting of the following components: (a) self-reported weight maintenance; (b) walking speed (the mean time of two trials for the time taken to walk 15 ft. reported in seconds); (c) grip strength, (mean score of grip strength reported in Lbs. of three trials on the dominant hand using a calibrated Jaymar dynamometer); (d) exhaustion, measured as a response of "All of the time" or "Most of the time" to the following two questions reported on a 4 point Likert scale, "I felt that everything I did was an effort in the last week," and "I could not get going in the last week"; and (e) total Kcals of energy expended over a 7 day period, measured via Community Healthy Activities Model Program for Seniors (CHAMPS) questionnaire. Change of all PA and MVPA duration (minutes/week) measured by CHAMPS. We also used Activpal to estimate the cumulated MVPA duration. We cumulated MVAP minutes by selecting activity intensity greater than 3 METs. Physical Function was measured via the Short Physical Performance Battery (SPPB) subtests for lower extremity strength and balance. Depressive symptoms were measured using the Geriatric Depression Scale (Kieffer & Reese, 2002). Participant anthropometry such as weight circumference (inch) was measured by a girthometer, height (cm) by a stadiometer, and weight (pound) by medical scales. Body mass index (BMI) was also calculated based on participant anthropometry. Quality of life was measured using the 26-item validated WHOQOL-BREF. Occupational performance was

measured by the Canadian Occupational Performance Measure (COPM), but only among treatment group participants. Habit Formation was measured using the validated, 4-item, Self-Report Behavioral Automaticity Index (SRBAI). The SRBAI measures perceptions of behavioral automaticity for an identified behavior. To track habit formation during the intervention, the SRBAI was administered to treatment condition participants every 2 weeks from sessions 3-11 to assess changes in automaticity for their self-selected habits.

3. Potential Benefits, Risks and Alternatives

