1.3.5 Randomization and Blinding

After consent/baseline evaluation visit. The study coordinator will check participants' eligibility. Randomization was carried out by a coordinator not involved in data collection or analysis activities. Data collectors were blinded to arm assignment.

Participants will be allocated using a 1:1 ratio via adapted randomization sequences generated *a priori* by the study statistician, [name], using an online tool (<https://www.sealedenvelope.com/simple-randomiser/v1/lists>) to form a randomization table with a variable block size (2,4, or 8). Randomization sequence concealment will be achieved by query of the REDCap (Research Electronic Data Capture) system.

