1.3.7 Intervention period

The treatment group will receive habit formation intervention for 12 weeks. The HF intervention is delivered by an experienced geriatric occupational therapist. The 12-week long, intervention is delivered to each participant during 12 face-to-face, home based sessions (each lasting ~60 minutes). An initial session (week 2) focuses on welcoming the participant to the program, and delivering educational content about prefrailty, frailty protective behaviors, and the concept of HF. In preparation for the sessions covering ST reduction and MVPA the next session (week 3) focuses on pain, its management, and the relationship between pain and activity (described below). Weeks 3-11 include weekly HF sessions focused on ST reduction, MVPA and dietary behaviors (see Table 2 for session content). A closing session occurs in week 12 to review program progress and create maintenance plans.

The control group will receive 12 weeks of newsletters focused on general healthy aging topics. Within 4 days of mailing the newsletter, the coordinator will call the participant, verify receipt of the newsletter, and ask them if they have any questions about the materials. Phone

call will last ~15 minutes. Control condition participants receive no further intervention.

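### The prefrailty outcome includes self-reported CHAMPS activity, which overlaps with what the treatment arm is coached to do, and no component-level analysis is planned to show what moved

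*Combined protocol and SAP*

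**What the plan says.** Entry requires participants to be "prefrail (evaluated by the Fried's Frailty Criteria Index") (1.3.1). Hypothesis 2 (1.1) lists among its "secondary outcomes (prefrailty reduction, lower extremity strength, balance, and quality of life"). Table 1 (1.3.8) schedules the Fried criteria at baseline and follow-up.

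Section 2.3 defines the outcome: "Pre-frailty status was measured using the current gold standard, the Cardiovascular Health Study frailty criteria as composite index". Its five components are weight maintenance, walking speed, grip strength, exhaustion and "total Kcals of energy expended over a 7 day period, measured via Community Healthy Activities Model Program for Seniors (CHAMPS) questionnaire". The same questionnaire, "Community Healthy Activities Model Program for Seniors (CHAMPS"), appears in Table 1 as a sedentary-time measure, and 2.3 also uses it for PA and MVPA duration.

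On the arms, 1.3.7 says of the treatment group: "Weeks 3-11 include weekly HF sessions focused on ST reduction, MVPA and dietary behaviors". For the comparator: "The control group will receive 12 weeks of newsletters focused on general healthy aging topics", with short follow-up calls. On blinding, 1.3.5 says only: "Data collectors were blinded to arm assignment".

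Section 2.1 summarises primary and secondary outcomes by Cohen's d. It plans no analysis of frailty by component and none without the activity item.

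**The concern.** Section 1.2 argues that physical activity protects against frailty by limiting muscle loss and by raising strength and physical performance. Prefrailty reduction is then offered as a consequence of the behaviour change. As scored, one fifth of the index is the behaviour itself, reported by participants who are not described as blinded, and the treatment arm is coached on that behaviour far more intensively than the control arm. Randomization does not remove a difference that coaching creates in one arm after allocation.

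What is at stake is interpretation. With the index summarised by a single d, a favourable result could mean stronger or faster participants, participants who are truly more active, or participants who report more activity. The planned output would not tell a reader which.

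**Working it through.** The plan states no figure on this point, so there is none to reproduce. The check traces the component through the plan and then illustrates its possible size.

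**Step 1. Source of each component (2.3, 1.3.5, 1.3.7).**

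| Component | Source | Direct target of coaching? |
|---|---|---|
| (a) Weight maintenance | Participant's answer | No (diet is coached) |
| (b) 15-ft walk time | Measured by blinded data collector | No |
| (c) Grip strength | Measured by blinded data collector | No |
| (d) Exhaustion | Participant's answer | No |
| (e) 7-day kcal, CHAMPS | Participant's answer | Yes (activity, sedentary time) |

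That the Fried index in 1.3.1 is the five-component index in 2.3 is an inference. It rests on Table 1, which lists the Fried criteria with grip strength and the 15-ft walk.

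**Step 2. What the index can and cannot show.** Assume that one positive component is enough to count as prefrail; the documents do not state the threshold. A participant positive on (e) alone moves from 1 to 0 by reporting activity above the cut, with walk time and grip unchanged. A participant positive on (e) and grip moves from 2 to 1: a lower count, but no full reversal. In both cases the index improves with no change in measured performance.

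**Step 3. Possible size, on assumed inputs.** The documents give none of the following:

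- q = share prefrail through (e) alone: 0.10 to 0.60
- f = share positive on (e) at baseline, alone or with others: 0.25 to 0.75
- rT − rC = treatment-minus-control difference in the share of those participants whose CHAMPS answer crosses the cut: 0.20 to 0.50
- SD of change in the component count: 0.6 to 1.0

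The other four components are held fixed.

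On the component count, d = f × (rT − rC) / SD:

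- low: 0.25 × 0.20 / 1.0 = 0.05
- high: 0.75 × 0.50 / 0.6 = 0.625

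If reversal were analysed as a proportion (the plan states no such rule), the between-arm difference = q × (rT − rC):

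- low: 0.10 × 0.20 = 0.02, or 2 percentage points
- high: 0.60 × 0.50 = 0.30, or 30 percentage points

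In participants, that is 15 × 0.02 = 0.3 to 15 × 0.30 = 4.5 at the 15 per group of section 2.2. At 40 per arm (the 80 in section 1.3, allocated 1:1) it is 40 × 0.02 = 0.8 to 40 × 0.30 = 12. The two sample sizes do not agree and must be reconciled separately.

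**Step 4. Precision.** The approximate 95% half-width for d near 0 is 1.96 × √(2/n):

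- n = 15 per arm: 0.72
- n = 40 per arm: 0.44

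The assumed contribution of (e) runs from negligible to above the 0.5 that section 2.1 calls moderate. At 15 per group, the half-width exceeds that whole range.

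**The case against.** The strongest reply is that activity belongs to this index. The plan adopts an established instrument, and 1.2 defines frailty across domains of functioning, not by strength alone. A true rise in activity should move the score. This stands: a reader might infer that the outcome was wrongly chosen, and the documents do not support that.

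The plan also collects independent checks. SPPB lower-extremity strength and balance are secondary outcomes in their own right, ActivPal gives device-measured sedentary time and MVPA, and walk time and grip are recorded in seconds and pounds. This stands in part. The data exist, but 2.1 does not say they will be set beside the frailty result or that the components will be reported.

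The contrast between arms can be overstated. Section 3.1 says all participants receive information on raising activity or improving diet, and it calls the comparator an attention control. The sessions in weeks 3 to 11 are also shared among sedentary time, MVPA and diet. The arms still differ, because newsletters with short calls are not weekly coaching, but the control arm is not untouched. Some controls will cross the activity cut too, so a shift computed in the treated arm alone would overstate the effect.

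Finally, this is a feasibility pilot with no efficacy power, and frailty is a secondary outcome. That limits the priority of the point without answering it.

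**Conclusion.** The overlap is in the text, and so is the absence of any analysis that would resolve it. A between-arm Cohen's d on the five-component index cannot by itself separate improved strength or walking speed from real or merely reported activity change.

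The size is unknown. The range of d from 0.05 to about 0.6 rests wholly on assumed prevalence, crossing rates and SD, and it starts at negligible. A reader might infer that any prefrailty reduction seen here would be spurious. The documents do not support that: they show a route to misreading, not that participants will take it. Those positive on another component would not fully revert by this route, and real activity change also moves the item.

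A reader might also want to accept Hypothesis 2 only if the direction of effect holds without component (e). That rule would be weak. With no true effect, direction alone is close to a coin toss, and anyone who entered on (e) alone starts at zero on the reduced index and can only stay there or worsen.

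This is a cheap improvement to reporting, not a fault in the choice of outcome.

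**What to change.** Keep the five-component index as the stated outcome. In 2.1 add, from data already collected:

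1. Each frailty component by arm at baseline and follow-up, with the criteria each participant met at entry.
2. 15-ft walk time and grip strength as continuous between-arm effect sizes with confidence intervals.
3. A sensitivity analysis of the index without component (e), with a note that participants who entered on (e) alone cannot improve on it.
4. ActivPal MVPA beside the CHAMPS activity result.

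State in advance that if the index changes only through component (e), the result will be described as activity change and not as restored physical function.

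The cost is plan wording and one extra table, with no new data. The downside is that the sensitivity version is less comparable with published indices and may show a smaller effect. Weight maintenance and exhaustion remain self-reported in it, so items 1 and 2 carry most of the interpretive weight.
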